5. STUDY DESIGN

5.1. Overall Design

This is a multi-centre, randomised, double blind (sponsor open), placebo-controlled, repeat-dose, proof of mechanism study of subcutaneous administrations of GSK2330811 in males and females with dcSSc.

The study includes two sequential cohorts. Cohort 1 is planned to consist of at least 4 participants and will evaluate a repeat-dose predicted to provide sub-maximal inhibition of OSM, leading to a dose escalation decision once at least 4 participants have reached the end of the treatment period (see Section 7.2). Cohort 2 will then evaluate a repeat-dose, predicted to provide maximal inhibition of OSM, to test POM. The study design, for both cohorts, is depicted in Figure 1.

Figure 1 Study Schematic

- Participants who consent will attend the clinical facility for screening and if eligible will enter the treatment period of the study within 42 days.
- The screening period will be at least 28 days for WOCBP to allow for a minimum 28 day interval between the screening and Day 1 pregnancy tests.
- Participants will be randomised in a 3:1 ratio within each cohort to GSK2330811 and placebo respectively. In cohort 2 treatment allocation will be stratified according to mycophenolate concomitant medication status (treated or non-treated).
- Participants will attend the clinical facility to receive a subcutaneous dose of GSK2330811 or placebo on Day 1 and then every other week until the sixth and final dose at the Day 71 (Week 10) visit.
- A Data Review Committee (DRC) will be responsible for determining progression from cohort 1 to cohort 2 as described in Section 7.2.
- Interim analyses will be conducted during cohort 2. The rationale, conduct and potential outcomes of these are described in Section 10.3.3.
- Study safety monitoring will be undertaken in a blinded manner by the Sponsor Safety Review Team (SRT) as described in Appendix 3. The Study Medical Monitor will also continuously review adverse events and laboratory tests for individual participants during the conduct of the study to ensure individual participant monitoring.
- Skin biopsies will be collected to assess GSK2330811 pharmacology and biomarkers at the site of action. Two punch biopsies will be collected from involved skin, on the forearm of participants, on both Day 1 and during the Day 85 (Week 12) visit window.

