9.8.2. Exploratory Biomarkers in Skin Biopsy

Two skin punch biopsies, 3 mm in size, will be collected from clinically involved skin (mRSS \geq 1), preferably hairless, on the forearm of participants, on Day 1 (pre-dose) and also on Day 85. All biopsies for a participant should be collected from the same forearm following SRM recommendations. At both timepoints, one biopsy sample will be evaluated histologically while the second biopsy sample will be evaluated by transcriptomic analysis. Biopsy quality assessments may be performed during the study

as described in the SRM. Details of the biomarker skin biopsy sample processing, storage, quality assessments and shipping procedures are provided in the SRM.

Histopathological assessments of the biopsy will explore changes in levels of disease biomarkers (protein and / or mRNA and / or pathological evaluation) in response to GSK2330811. Markers may include (but are not restricted to):

- Fibrosis markers, such as α SMA to assess changes in myofibroblast numbers.
- Inflammation markers, such as changes in numbers of CD3+ T cells.
- Vasculopathy markers, such as changes in CD31+ endothelial cells.

Transcriptomic analysis will determine the effect of GSK2330811 on OSM and disease related gene expression. Gene expression will be measured using microarray technology, and/or alternative equivalent technologies, which facilitates the simultaneous measurement of the relative abundances of thousands of RNA species resulting in a transcriptome profile for a skin biopsy sample. The same samples may also be used to confirm findings by application of alternative technologies. Genes may include but are not restricted to:

- OSM related genes such as SOCS3 and JAK2.
- Fibrosis markers, such as THBS1 and COMP.

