10.3.2. Other Analyses

PK, pharmacodynamic and biomarker exploratory analyses will be described in the RAP.

The analysis approach for exploratory biomarkers will be:

- Relationships between endpoints, explored graphically and using statistical measures of consistency if data allow.
- Profiles / Trends over time of individual endpoints

- Inference using posterior probabilities of the true within participant change from baseline and true between group treatment difference using non-informative prior distributions.

In addition to the univariate analysis of the change from baseline in each biomarker, a multivariate analysis of endpoints of several biomarkers of fibrosis may also be performed.

The primary between-group analysis will be between the placebo and GSK2330811 groups. However if a difference in baseline levels of key biomarkers of fibrosis is observed by mycophenolate use then an alternative primary comparison will be considered.

The following PK/PD analyses will be conducted if data permit:

- To examine the relationship between plasma concentrations of GSK2330811, and target OSM concentration (total).
- To examine the relationship between plasma concentrations of GSK2330811, and platelet count.

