13.1.1.2. Skin Histology

• Alpha Smooth Muscle Actin (αSMA)

(Note: During the review process of Alpha SMA samples, some samples were found to have insufficient tissue due to shallow biopsies. Summaries, stats analysis and plots exclude those insufficient samples. Additional summary and plots will be produced on the full data (including both the sufficient and insufficient samples.)

13.1.1.3. Skin Gene expression RNA Sequencing:

13.1.1.3.1. Individual Genes of Interest:

- Inflammation genes: CCL2, CCL18, MS4A4A
- Fibrosis genes: THBS1, COMP
- PD marker at the site of action: SOCS3
- Target expression in skin: OSM, OSMR

13.1.1.3.2. Derived Gene:

• 2-gene SSc skin biomarker: 2GSSc (See Section 16.6.6 for derivation)

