13.1.5. Statistical Analyses / Methods

Details of the planned displays are provided in Appendix 12 and will be based on GSK Data Standards and statistical principles.

The endpoints / variables defined in Section 13.1.1 will be summarised using descriptive statistics, graphically presented (where appropriate) and listed.

Longitudinal model

The ratio to baseline for the following systemic biomarkers will be analysed using a Bayesian MMRM analysis using the log transformed data including only the placebo and GSK2330811 300mg arms:

- Pro-C3
- Pro-C6
- PINP
- ELF
- COMP
- PIIINP
- IL-6
- MCP-1 (Rename MCP-1 as CCL2 for displays)
- CCL-18

Non-informative priors will be used in these analyses, specifically the prior for the regression coefficient will be normally distributed with mean 0 and a variance of 10^6 . The variance-covariance matrix for the within subject error across the visits will use an inverse-Wishart prior distribution, consisting of the identity matrix and the degrees of freedom will be the number of visits included in the model.

The models will be adjusted for the following covariates: MMF use at day 1, baseline value, treatment, visit, treatment by visit and baseline by visit interactions.

201247

The change from baseline within each treatment group and the difference in the change from baseline across the treatment groups (GSK2330811 300mg – placebo) will be calculated and are back transformed to give the ratio to baseline and the ratio of the change relative to placebo respectively.

Posterior medians and equal tailed 95% credible intervals will be presented. In addition, the probability the ratios are <1 and fold changes (Posterior Medians, as ratio < 1 then fold change is -1/ratio otherwise fold change is ratio) will also be calculated. The line plot of the adjusted posterior medians \pm credible intervals at each visit will be presented.

ANCOVA

The ratio to baseline of log transformed and change from baseline of linear data for the following skin histology and gene expression mRNA sequencing endpoints will be analysed using a Bayesian ANCOVA analysis including only the placebo and GSK2330811 300mg arms:

- Alpha SMA (Excluding Insufficient samples)
- COMP
- CCL2
- 2GSSc
- Disease Signatures GSVA Scores (Upregulated and Downregulated)
- Lung Fibrosis Signature GSVA Score
- Cell Modular Signatures GSVA Scores (Fibrosis, M1-Macrophage and M2-Macrophage)

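### SOCS3, the SAP's designated PD marker in skin, is only described by arm; no model in this SAP estimates 300 mg against placebo for it

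*SAP*

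**What the plan says.** The protocol gives cohort 2 a mechanistic purpose (Section 5.1): "Cohort 2 will then evaluate a repeat-dose, predicted to provide maximal inhibition of OSM, to test POM". For the skin biopsies, Section 9.8.2 states: "Transcriptomic analysis will determine the effect of GSK2330811 on OSM and disease related gene expression". It then gives examples, among them "OSM related genes such as SOCS3 and JAK2". For exploratory biomarkers, Section 10.3.2 includes in the approach: "Inference using posterior probabilities of the true within participant change from baseline and true between group treatment difference using non-informative prior distributions".

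SAP Section 13.1.1.3.1 names eight individual skin genes of interest. CCL2, CCL18 and MS4A4A are listed as inflammation genes, and THBS1 and COMP as fibrosis genes. The other two entries are "PD marker at the site of action: SOCS3" and "Target expression in skin: OSM, OSMR".

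SAP Section 13.1.5 then specifies three Bayesian biomarker models, each limited to placebo and 300 mg:

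- Longitudinal: "The ratio to baseline for the following systemic biomarkers will be analysed using a Bayesian MMRM analysis" (nine blood markers).
- ANCOVA at Day 85: the listed "skin histology and gene expression mRNA sequencing endpoints will be analysed using a Bayesian ANCOVA analysis" (alpha SMA, COMP, CCL2, 2GSSc, and six GSVA scores for the disease, lung fibrosis and cell-module signatures).
- Joint model: alpha SMA, skin CCL2, serum PIIINP and 2GSSc.

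In Appendix 12, Tables 8.9 and 8.10 and Figures 8.10 and 8.12 cover the individual genes descriptively. Table 8.11 holds the model results and is restricted to the endpoints specified in Section 13.1.5. Figure 8.11 plots adjusted values, which exist only for modelled genes.

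**The concern.** The protocol keeps two things apart. Section 5.4 speaks of mRNA markers of the drug's pharmacology in skin biopsies, and separately of biomarkers of fibrosis, inflammation and vasculopathy. Section 9.8.2 makes the same distinction between OSM-related and disease-related genes. Every skin endpoint that receives a model is on the disease side. The one gene that the SAP itself labels as the PD readout in skin is left to description.

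This matters most if the disease markers do not move by Week 12. A reader would then ask whether the pathway was not inhibited in skin, or was inhibited without a disease effect. SOCS3 is informative here because it comes from paired Day 1 and Day 85 biopsies in both arms. Serum target engagement does not settle the matter: Protocol Section 5.5 states its predictions for serum at trough, and reports mean drug concentration in blister fluid at 19 to 45% of that in plasma. As planned, the SOCS3 comparison would be made by eye between unadjusted arm summaries, with perhaps five or six placebo participants. It would lack the baseline and mycophenolate adjustment that the SAP applies to the other modelled skin endpoints.

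**Working it through.** **Step 1. Can SOCS3 enter a model directly or indirectly?**

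| Place in the SAP | Content | SOCS3? |
|---|---|---|
| 13.1.5, longitudinal model | nine systemic markers | no |
| 13.1.5, ANCOVA | alpha SMA, COMP, CCL2, 2GSSc, six GSVA scores | no |
| 13.1.5, joint model | alpha SMA, skin CCL2, PIIINP, 2GSSc | no |
| 14.1.5, efficacy models | mRSS, HAQ-DI, FVC, CRISS | no |
| 16.6.6, 2GSSc formula | THBS1 and MS4A4A | no |
| Appendix 13, gene sets | 42 down and 209 up (disease), 42 (lung fibrosis), 31 / 32 / 37 (M2, M1, fibrosis modules) | no |
| 14.1.5, clinical-against-biomarker correlation pairs | baseline skin OSM appears, as a correlate | no |

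Of the eight individual skin genes, two (COMP, CCL2) are modelled directly. Two (THBS1, MS4A4A) enter only through composite scores. Four (CCL18, SOCS3, OSM, OSMR) are not modelled in skin. All three OSM-axis genes are in the last group. SAP Table 1, which lists changes from the protocol's analysis plan, does not mention this.

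**Step 2. Reproduce the only between-arm precision figure in the documents.** Protocol Section 10.1 gives SD 0.521 for log(PIIINP), 15 active and 5 placebo participants, two-sided 5%, and a half-width of 0.565.

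Half-width = t(0.975, 18) × SD × √(1/15 + 1/5) = 2.101 × 0.521 × 0.5164 = 0.565. This agrees.

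**Step 3. Precision if SOCS3 joined the ANCOVA.** The model has an intercept, treatment, mycophenolate use and baseline, so the error degrees of freedom are N − 4. The priors are vague, so a t interval approximates the credible interval. In units of the residual SD:

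Half-width = t(0.975, nA + nP − 4) × √(1/nA + 1/nP)

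| Active / placebo | Basis | Half-width (residual SD) |
|---|---|---|
| 15 / 5 | cohort 2 at its minimum of about 20, 3:1 | 1.09 |
| 15 / 6 | same, plus one cohort 1 placebo participant | 1.02 |
| 27 / 9 | cohort 2 at its maximum of 36, 3:1 | 0.78 |

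**Step 4. Fold scale.** The documents give no SD for SOCS3, so a range is assumed. With 15 against 5, the interval is the estimate multiplied or divided by 2^(1.0947 × SD):

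| Assumed residual SD (log2 units) | Factor |
|---|---|
| 0.5 | 1.46 |
| 0.75 | 1.77 |
| 1.0 | 2.14 |
| 1.5 | 3.12 |

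These figures ignore covariate imbalance and unusable biopsies, both of which would widen the interval.

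**The case against.** The case on the other side has real weight.

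- **Other skin contrasts are planned.** A reader might infer that the trial plans no between-arm estimate of any pathway effect in skin. The documents do not support that. The SAP models alpha SMA, COMP, CCL2, 2GSSc and six signature scores, and Protocol Section 3.1 treats fibrosis, inflammation and vasculopathy markers as mechanistic. The gap is confined to the direct OSM-axis genes.
- **Blister fluid also bears on the question.** A reader might infer that only a skin pathway gene could separate lack of inhibition from inhibition without effect. Protocol Section 9.8.3 plans drug, total OSM and free OSM in blister fluid, from at least six participants on active drug. These data are limited: the procedure is optional, confined to selected sites and cohort 2, and has no baseline. The final displays are listings (43 and 45), although the values also enter the PK/PD dataset. They are still relevant evidence.
- **SOCS3 is not ignored.** It has ratio-to-baseline summaries by arm, plots of geometric means with standard errors, and individual profiles marked by mycophenolate use. What is missing is the modelled contrast.
- **More may follow.** SAP Section 13.1.5 defers further transcriptomics to a separate plan that is not among these documents. It may cover SOCS3, but nothing here says that it does or when it is fixed.
- **The endpoint is exploratory.** No formal hypothesis is tested, and the protocol's gene list is illustrative. For that reason the absence of JAK2 from the SAP's genes of interest, which a reader might take for a breach, is not one.

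Low precision is a weaker objection, because the endpoints already in the ANCOVA face the same sample size.

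**Conclusion.** The point holds for this SAP, and for the direct OSM-axis skin genes. SOCS3 carries the SAP's own PD label, yet receives no estimate of 300 mg against placebo, no credible interval and no posterior probability. Protocol Section 10.3.2 names posterior inference on the between-group difference as the approach for exploratory biomarkers, and the SAP gives no reason for treating SOCS3 differently. It is a gap in an exploratory analysis, not an error in a confirmatory one, and it does not touch the primary safety objective.

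A modelled contrast would be imprecise, at about 0.8 to 1.1 residual SD either side of the estimate for the sample sizes considered. Whether a plausible SOCS3 effect would stand out cannot be judged, because the documents give neither its SD nor a target effect. The half-widths assume that nearly all participants supply usable paired biopsies and that the vague priors add almost no information.

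**What to change.** Add SOCS3, as log2 ratio to baseline, to the Day 85 Bayesian ANCOVA list in SAP Section 13.1.5. It then carries through to Table 8.11 and Figure 8.11, with the outputs already specified for log-transformed endpoints: ratio to baseline, ratio to placebo, 95% credible interval, fold change and the probability that the ratio is below 1. Make the change before the randomisation codes are released for the final analysis. OSM and OSMR can stay descriptive, since the SAP labels them as target expression and not as a PD response.

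If the sponsor prefers to keep SOCS3 descriptive, the SAP should say why, and whether the separate transcriptomics plan will specify the contrast before unblinding.

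The cost is one list entry and one more run of an existing model on data already being collected. The downside is one more exploratory posterior without multiplicity adjustment, which is consistent with SAP Section 5.6.

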5.3.1. Derivations and Handling of Missing Baseline Data

Definition	Reporting Details
Change from Baseline	= Post-Dose Visit – Baseline
% Change from Baseline	= 100 x [(Post-Dose Visit – Baseline) / Baseline]
Ratio to baseline	= Post-Dose Visit / Baseline
Nadir	= Lowest post-baseline value of endpoint for a participant ^[1]
Days to Nadir	= Study Day of Nadir – 1 ^[1]
Maximum Change from Baseline	 Calculate the change from baseline at each given timepoint and determine the maximum absolute change
Minimum value at timepoint	= The lowest value of the parameter in the reported group at the specified timepoint.

NOTES:

- 1: When there are multiple instances of the lowest value then the nadir used for reporting will be the earliest occurrence of that value.
- Unless otherwise specified, the baseline definitions specified in Section 5.3 Baseline Definitions will be used for derivations for endpoints / parameters and indicated on summaries and listings.
- Unless otherwise stated, if baseline data is missing no derivation will be performed and will be set to missing.
- The baseline definition will be footnoted on all absolute summary and change from baseline plots. 'Note: Baseline
 is defined as the pre-dose Day 1 assessment, unless unavailable, in which case it is the latest pre-dose
 assessment.'
- If there are multiple measurements (i.e. ECG) the derivation will be based on the average values where available.

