Non-informative priors will be used in these analyses, specifically the prior for the regression coefficient will be normally distributed with mean 0 and a variance of 10^6 . The prior for the variance parameter will be an inverse-gamma (shape=0.001, scale=0.001).

The models will be adjusted for the following covariates: MMF use at day 1, baseline value and treatment.

Nature of Data	Output Presentation
Log Transformation	 The change from baseline and difference in the treatment groups (GSK2330811 300mg – placebo) will be back transformed to give ratio to baseline and ratio of the change relative to placebo respectively. Posterior medians, equal tailed 95% credible intervals, probability that ratios < 1 and fold change (i.e., Posterior Medians, as ratio < 1 then fold change is -1/ratio otherwise fold change is ratio) will be presented.
Linear	 Change from baseline and the difference in the treatment groups (GSK2330811 300mg – placebo) will be calculated. Posterior medians and equal tailed 95% credible intervals will be presented. Except for Downregulated GSVA score, the probability that difference < 0 will be calculated. For Downregulated GSVA score, the probability > 0 will be calculated.
201247

The plot of the adjusted posterior medians \pm credible intervals along with individual ratio to baseline or change from baseline values based on the endpoints will be presented.

Joint model

In addition to the Bayesian MMRM analysis, the ratio to baseline or change from baseline based on the endpoints for the following four key biomarkers will be modelled using a multivariate Bayesian analysis including only the placebo and GSK2330811 300mg arms:

- Alpha SMA (Excluding Insufficient samples)
- CCL2 gene assessed from the skin sample through RNA sequencing
- PIIINP assessed from the serum sample
- 2GSSc

Non-informative priors will be used for all parameters. The variance-covariance matrix for the within subject error across the endpoints will use an inverse-Wishart prior distribution consisting of the identity matrix and 4 degrees of freedom.

The model will be adjusted for endpoint (allows each endpoint to have their own intercept), treatment by endpoint interaction term, MMF use at day 1 by endpoint interaction, and baseline by endpoint interaction term. If the model does not converge, the covariate for MMF use will be removed from the model.

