Missing baseline covariates will be modelled as part of the MCMC sampling prior to fitting the joint model, using non-informative priors. For example, if b_i is the baseline of the ith endpoint then $b_i \sim N(\theta_i, \delta_i)$ where $\theta_i \sim N(0, sd=100)$ and $\delta_i \sim iGamma(shape=0.1, scale=0.1)$.

For modelling purposes, the log transformed endpoints will be back transformed for the presentation of results. Fold change will also be presented for only log transformed endpoints, posterior medians as, ratio < 1 then fold change is -1/ratio otherwise fold change is ratio.

Heat Plots

Heat plots will be produced for the gene expression endpoints contributing to a gene signature using fold change from baseline. Fold change in Placebo, GSK2330811 100mg and GSK2330811 300 mg at day 85 will be presented in three columns using the 3-fold change cut off. Plot colour scales from blue to white to red scale, values above 3 or below -3 fold change will all be presented using the same colour.

Heat plots are produced for each individual gene from Disease Signature, Lung Fibrosis signature and Cell module signatures as mentioned in Section 13.1.1.3. Within each signature, genes are ordered based on 'Ward' clustering algorithm.

For further reference, heat plot with dendogram for full gene panel contributing to the different signatures will be produced and saved in Refdata folder.

201247

Additional Post SAC transcriptomics analysis will be conducted and the details will be documented in a separate analysis plan.

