16.7.2.2. Handling of Missing Data for Statistical Analysis

For the joint model, missing baseline data will be modelled as part of the MCMC sampling, no post baseline data will be imputed. For all other models, missing data will not be imputed.

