8.12	Per Protocol	BIO_T9	Summary of Ratio to Baseline in mRNA Gene Expression Results at Day 85: Disease Signature Genes	By gene sets, gene and treatment.	SAC				
8.13	Per Protocol	BIO_T9	Summary of Ratio to Baseline in mRNA Gene Expression Results at Day 85: Lung Fibrosis Signature Genes	By gene, by treatment.	SAC				
8.14	Per Protocol	BIO_T9	Summary of Ratio to Baseline in mRNA Gene Expression Results at Day 85: Cell Module Signature Genes	By gene sets, gene and, by treatment.	SAC				
Biomarker: Tables									
-------------------	-----------------	----------------------------	--	--	---------------------------	--	--		
No.	Population	IDSL / Example Shell	Title	Programming Notes	Deliverable [Priority]				
8.15	Per Protocol	BIO_T10	Summary of mRNA Gene Signature Results		SAC				
8.16	Per Protocol	BIO_T10	Summary of the Change from Baseline in mRNA Gene Signature Results at Day 85	Page by 2GSSc and GSVA scores. This include 2GSSc, Disease, Lung Fibrosis and Cell module Signatures.	SAC				
8.17	Per Protocol	BIO_T11	Analysis of the Change from Baseline in mRNA Gene Signature Results at Day 85	Ĵ	SAC				
Joint model	of key biomar	kers							
8.18	Per Protocol	BIO_T5	Joint Model of Ratio to Baseline in Key Biomarkers at Day 85		SAC				
8.19	Per Protocol	BIO_T6	Joint Probabilities for Key Biomarkers at Day 85		SAC				
Correlation of	of Biomarkers								
8.20	Safety	BIO_T4	Correlation of Baseline Levels of Systemic Biomarkers	Baseline values only. No treatment groups. Exclude C1M results using mouse hybridoma cell line as small sample size may be unblinding. Add footnote 'Note: C1M assay changed during the study. C1M results not presented for samples analysed using the old C1M (denoted C1M*) kit due to small sample size and potential unblinding. New C1M kit denoted as C1M+.'	IA2				
Mechanistic	Haematology/	Chemistry							
8.21	Safety	SAFE_T1	Summary of Mechanistic Haematology/ Chemistry	Refer to Section 7.2 'Group 2' for	SAC				

Biomarker: Tables							
No.	Population	IDSL / Example Shell	Title	Programming Notes	Deliverable [Priority]		
8.22	Safety	SAFE_T1	Summary of Change from Baseline in Mechanistic Haematology/ Chemistry	list of endpoints	SAC		
8.23	Safety	SAFE_T1	Summary of Percentage Change from Baseline in Mechanistic Haematology/ Chemistry		SAC		

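### The joint biomarker model's change-from-baseline outcome drops a valid Day 85 alpha SMA value if the Day 1 section is insufficient, although the SAP already models the missing baseline

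*SAP*

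**What the plan says.** - **Outcome.** In SAP section 13.1.5, under Joint model, "the ratio to baseline or change from baseline based on the endpoints for the following four key biomarkers will be modelled": alpha SMA (excluding insufficient samples), skin CCL2, serum PIIINP and 2GSSc, in the placebo and 300 mg arms only. Table 8.18 in Appendix 12 is titled "Joint Model of Ratio to Baseline in Key Biomarkers at Day 85".
- **Covariates.** Each endpoint has its own intercept, treatment effect and mycophenolate effect, and a "baseline by endpoint interaction term".
- **Missing baseline, general rule (SAP 5.3.1).** "Unless otherwise stated, if baseline data is missing no derivation will be performed and will be set to missing".
- **Missing baseline, joint model (SAP 13.1.5).** "Missing baseline covariates will be modelled as part of the MCMC sampling prior to fitting the joint model, using non-informative priors".
- **Missing data (SAP 16.7.2.2).** "For the joint model, missing baseline data will be modelled as part of the MCMC sampling, no post baseline data will be imputed".
- **Biopsy quality (SAP 13.1.1.2).** For alpha SMA, "some samples were found to have insufficient tissue due to shallow biopsies", and "Summaries, stats analysis and plots exclude those insufficient samples".

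**The concern.** The SAP provides a model for missing baselines but applies it, in terms, only to the covariate. The same baseline is also inside the outcome. If the outcome is missing because its baseline is missing, a sampled covariate value has no alpha SMA observation to explain. The observed Day 85 section then adds nothing to the alpha SMA treatment effect.

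Alpha SMA is the only histology endpoint and one of the four key biomarkers. The placebo group has only five or six participants, so each placebo value counts. Under the non-convergence steps in SAP section 13.1.5.1, the endpoint with the most missing data is removed from the joint model. Outcomes lost in this way could add to alpha SMA's exposure to that step.

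**Working it through.** **1. Does the text lose the value?**
- The outcome for alpha SMA is log Day 85 minus log baseline (13.1.5, Table 8.18).
- With no baseline, it is not derived (5.3.1).
- The exception in 13.1.5 concerns covariates. Nothing says that the sampled baseline forms the ratio, or that the raw Day 85 value enters the likelihood.
- The fallback to the latest pre-dose value (SAP 5.3) does not help, because the only scheduled pre-dose biopsy is on Day 1 (Protocol section 2).
- The Per Protocol exclusions (SAP 16.1.1) contain no biopsy criterion, so such a participant can stay in the analysis.
- Histology and RNA come from separate punches (Protocol 9.8.2), so the affected endpoint is alpha SMA, not CCL2 or 2GSSc.

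A one-endpoint Gibbs sampler with the SAP's baseline model confirmed this. With the change outcome, the treatment estimate matched that from deleting the participant (mean absolute difference 0.005 to 0.014, which is simulation noise).

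**2. Is the alternative outcome the same analysis when data are complete?** Write y for log Day 85, b for log baseline and X for the intercept, treatment and mycophenolate terms. Then y − b = Xβ + γb + e is the same equation as y = Xβ + (γ + 1)b + e. Only the baseline slope shifts, by 1. With vague priors the treatment coefficient is unchanged. A least-squares fit to one simulated dataset gave identical treatment coefficients.

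**3. The plan's own precision figure.** Protocol 10.1 gives 0.565 for log PIIINP (SD 0.521, 15 vs 5). Check: t(0.975, 18 df) × 0.521 × √(1/15 + 1/5) = 2.101 × 0.521 × 0.5164 = 0.565. This reproduces it. Complete-case losses under the same formula give 0.573 (14 vs 5), 0.619 (15 vs 4) and 0.699 (15 vs 3). Placebo losses cost most.

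**4. What a Day 85 value without its baseline is worth.** If ρ is the baseline to Day 85 correlation, it carries a fraction 1 − ρ² of a complete participant's information: 0.91, 0.75 and 0.51 at ρ = 0.3, 0.5 and 0.7. These correlations are assumed, as the documents give none. The arms are taken as 15 vs 6, that is 15 vs 5 in cohort 2 plus one cohort 1 placebo participant. To a first approximation, the variance is proportional to 1/I(active) + 1/I(placebo). At ρ = 0.5:
- One active baseline missing: deletion gives 1/14 + 1/6 = 0.2381; Day 85 as outcome gives 1/14.75 + 1/6 = 0.2345. The SD falls by 0.8%.
- One placebo baseline missing: 1/15 + 1/5 = 0.2667 against 1/15 + 1/5.75 = 0.2406. The SD falls by 5.0%.
- Three active missing: 1/12 + 1/6 = 0.2500 against 1/14.25 + 1/6 = 0.2368. The SD falls by 2.7%.

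**5. Simulation, one endpoint, 15 vs 6.** Fall in the SD of the treatment estimate over ρ = 0.3 to 0.7:

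| Missing baselines with a valid Day 85 value | Fall in SD |
|---|---|
| None | 0 |
| One, placed at random | about 1–3% |
| Three, all active | about 2–3% |
| Three, placed at random | about 4–7% |
| Five, placed at random | about 10–15% |

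Five of 21 is 24% of baselines, and nothing in the documents supports that many.

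The Gibbs sampler at 15 vs 5, with one placebo and one or three active baselines missing, gave credible intervals about 4–11% narrower. For example, at ρ = 0.5 the half-width went from 0.527 to 0.500 (one plus one) and from 0.653 to 0.584 (three plus one). It used only 12 datasets per setting, so these figures are rough.

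**The case against.** **The case may never occur.** A reader might infer from the note on shallow biopsies that Day 85 data are being discarded. The SAP does not show that. It gives no count and no visit. The loss needs an insufficient Day 1 section with a sufficient Day 85 section in the same placebo or 300 mg participant. If the poor samples were at Day 85, at both visits, or in the 100 mg arm, nothing is recovered. This objection stands, and it makes the size conditional.

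**The text is not airtight.** A reader might also infer that the SAP plainly orders these values to be dropped. Section 5.3.1 yields where something else is stated, and section 16.7.2.2 refers to missing baseline data, not only covariates. An analyst could form the ratio from the sampled baseline. The word covariates in 13.1.5 points the other way, so discarding is the natural reading but not the only one. The ambiguity itself needs a sentence.

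**The gain is not assumption-free.** With log Day 85 as the outcome, the alpha SMA estimate relies on the normal model for baselines and on baselines missing at random. Shallow biopsies make that plausible but do not prove it.

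**The simulations simplify.** They use one endpoint and no mycophenolate term. An information calculation with four endpoints (variances known, residual correlation 0.3 to 0.5 assumed) still gave a 3–7% fall in SD with three missing baselines, so borrowing across endpoints does not remove the gain. The effect on the joint probabilities in Table 8.19 was not computed.

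**Scope.** The separate alpha SMA ANCOVA does not impute missing data and is untouched by this change.

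**Conclusion.** The concern holds as a conditional point about precision. On the natural reading, the joint model recovers nothing for an endpoint whose baseline is missing, and a valid Day 85 alpha SMA value without a usable Day 1 section is lost. The fall in the SD of the treatment estimate is zero if no placebo or 300 mg participant has that pattern, about 1–3% with one, about 2–7% with three (least if all are active), and more only if more are missing. A single loss in the placebo arm would sit above that one-participant range, which averages over the arms. These figures rest on assumed correlations of 0.3 to 0.7, 15 vs 6 participants and single-endpoint simulation.

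No bias is claimed. The analysis is exploratory, no hypothesis is tested, and the sample size rests on feasibility. This is an optional refinement that costs almost nothing, not a defect that threatens a conclusion.

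**What to change.** In SAP section 13.1.5 (Joint model):
- Use log Day 85 as the outcome for alpha SMA and, for uniform coding, CCL2 and PIIINP. Keep the baseline-by-endpoint terms and the existing model for missing baselines.
- Leave 2GSSc as planned. Its formula (SAP 16.6.6) needs baseline THBS1 and changes from baseline, so it cannot be recovered.
- Report the treatment ratio as now. For Table 8.18, obtain within-group ratios to baseline by subtracting a stated reference, for example the pooled mean log baseline, from the adjusted Day 85 mean.

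Equivalently, keep the ratio as the outcome and state that it is formed from the sampled baseline within the MCMC. Under either wording, the missing baseline must be sampled jointly with the Day 85 data. The present wording, which places the baseline model before the joint fit, could be read as a separate earlier step, and the equivalence would then fail.

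Before deciding, count the placebo and 300 mg participants with an insufficient Day 1 section and a sufficient Day 85 section. If there are none, a clarifying sentence is enough.

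Cost: one paragraph and a small code change. No new data are needed, and the treatment estimate does not change when data are complete.
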